7.1.3 Unexpected AE or SAR

An AE or SAR is considered unexpected if the specificity or severity of it is not consistent with the applicable product information (e.g., Investigator's Brochure (IB) for an unapproved investigational product or package insert/summary of product characteristics for an approved product). Unexpected also refers to AEs or SARs that are mentioned in the IB as occurring with a class of drugs or as anticipated from the pharmacological properties of the drug, but are not specifically mentioned as occurring with the particular drug under investigation.

7.1.4 Serious AE or SAR

An AE or SAR is considered serious if, in the view of either the investigator or sponsor, it results in any of the following outcomes:

- Death;
- Is life-threatening (places the subject at immediate risk of death from the event as it occurred);

- Requires inpatient hospitalization (>24 hours) or prolongation of existing hospitalization;
- Results in congenital anomaly/birth defect;
- Results in a persistent or significant incapacity or substantial disruption of the ability to conduct normal life functions;
- Important medical events that may not result in death, be life-threatening, or require hospitalization may be considered a serious adverse drug experience when, based upon appropriate medical judgment, they may jeopardize the patient or subject and may require medical or surgical intervention to prevent one of the outcomes listed in the definition. For reporting purposes, also consider the occurrences of pregnancy as an event which must be reported as an important medical event.

7.2 Documentation of non-serious AEs or SARs

For non-serious AEs or SARs, documentation must begin from day 1 of study treatment and continue through the 30-day follow-up period after treatment is discontinued.

Collected information should be recorded in the Case Report Forms (CRF) for that patient. Please include a description of the event, its severity or toxicity grade, onset and resolved dates (if applicable), and the relationship to the study drug. Documentation should occur at least monthly.

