2.3.2 Secondary Study Outcome Variable

1. Improvement of QoL score at 6 months
2. Improvement of uroflowmetry (Qmax, PVR) at 6 months
3. Reduction of prostate volume at 6 months
4. Percentage of prostate infarcted at 6 months
5. Incidence of adverse events at 3 months

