4.1.10 Visit 5 - 3 Month Follow-Up

Subjects will return 90 +/- 14 days after PAE procedure to complete IPSS, and QOL questionnaires; to have Qmax and PVR measured; medication history questionnaires will be completed; and subjects will be evaluated for possible adverse events. It will be recorded if subjects are unable to hold medications at this time due to residual urinary symptoms. If an AE is suspected based on change in pain scores or functionality, an appropriate work-up will be performed.

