4.1.11 Visit 6 - 6 Month Follow-Up

Subjects will return 180 +/- 14 days after PAE procedure to complete IPSS with QOL and medication history questionnaires and to have Qmax and PVR measured. The subjects will be evaluated for possible adverse events. If an AE is suspected based on change in pain scores or functionality, an appropriate work-up will be performed.

An MRI of the prostate will be acquired.

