4.3 Time and Events Table

	Visit 1 (Screening)	Visit 2 (Procedure)	Visit 3 (1 Day)	Visit 4 (1 week)	Visit 5 (3 month)	Visit 6 (6 Month)	Visit 7 (12 month)
Informed Consent	X						
MRI	X					X	
PAE procedure		X					
IPSS w/QOL	X				X	X	X
Qmax	X				X	X	X
PVR	X				X	X	X
Medication History Questionnaire	X	X			X	X	
AE Assessment			X	X	X	X	

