7.0 ADVERSE EVENTS (DRUGS- CONTRAST AGENTS)

7.1 Definitions

7.1.1 Adverse Event (AE)

An adverse event (AE) is any untoward medical occurrence (e.g., an abnormal laboratory finding, symptom, or disease temporally associated with the use of a drug) in a patient or clinical investigation subject administered a pharmaceutical product and which does not necessarily have a causal relationship with this treatment. An AE can therefore be any unfavorable and unintended sign (including an abnormal laboratory finding), symptom, or disease temporally associated with the use of a medicinal product, whether or not related to the medicinal product.

Hospitalization for elective surgery or routine clinical procedures that are not the result of an AE (e.g., surgical insertion of central line) need not be considered AEs and should not be recorded as an AE. Disease progression should not be recorded as an AE, unless it is attributable by the investigator to the study therapy.

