7.3 SAEs or Serious SARs

7.3.1 Timing

After informed consent but prior to initiation of study medications, only SAEs caused by a protocol-mandated intervention will be collected (e.g. SAEs related to invasive procedures such as biopsies, medication washout).

For any other experience or condition that meets the definition of an SAE or a serious SAR, recording of the event must begin from day 1 of study treatment and continue through the 30 day follow-up period after treatment is discontinued.

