8.0 STATISTICAL CONSIDERATIONS

8.1 Study Design/Study Endpoints

The primary study aim is to determine if PAE is as effective as medication (non-inferiority) in reducing urinary symptoms due to BPH at 6 months.

This will be a single arm, non-blinded study of PAE using HydroPearl Beads in a small population with BPH to assess a clinically significant reduction in medications at 6 months. After IRB approval of a written informed consent and over, approximately a 24 month duration, N=30 subjects will be recruited. Only subjects ≥ 40 years will be screened for study recruitment. Clinical procedures and evaluations will consist of a preoperative screening assessment to determine if the potential study subject meets the inclusion and exclusion criteria, enrollment, surgical procedure for prostatic artery embolization (PAE), and follow-up visits at 24 hours, 1 week, 3, 6, & 12 months. An MRI will be performed after the 6-month visit in those patients who underwent embolization to detect a change in prostatic volume and perfusion and to exclude complication.

The study will be stopped if there is greater than one major complication (Grade D, E or F) as defined by the Society of Interventional Radiology Classification System for Complications by Outcome (29).

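### The 30-day AE and SAE recording window has an undefined end and contradicts the 6-month AE assessment, Section 9.3.1 and, if counted from PAE, the 3-month AE outcome

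*Combined protocol and SAP*

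**What the plan says.** The Combined protocol and SAP sets the recording period in two places:

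- Section 7.2, non-serious events: "documentation must begin from day 1 of study treatment and continue through the 30-day follow-up period after treatment is discontinued".
- Section 7.3.1, serious events: "recording of the event must begin from day 1 of study treatment and continue through the 30 day follow-up period after treatment is discontinued".

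Both stand under a Section 7 heading that reads "ADVERSE EVENTS (DRUGS- CONTRAST AGENTS)".

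Other sections look for adverse events later, or without a limit:

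- Section 2.3.2 lists as a secondary outcome "Incidence of adverse events at 3 months".
- Section 4.1.10 (3-month visit, day 90 +/- 14): "subjects will be evaluated for possible adverse events".
- Section 4.1.11 (6-month visit, day 180 +/- 14): "The subjects will be evaluated for possible adverse events".
- Section 4.3: the row "AE Assessment" is marked at 1 day, 1 week, 3 months and 6 months, and not at 12 months.
- Section 9.3.1 has all adverse events recorded and summarised for the final manuscript, and has complications graded major or minor on the CRF. Neither statement carries a time limit.
- Section 8.1: "The study will be stopped if there is greater than one major complication", with no period attached.

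Section 8.3 compares the proportion of patients with AEs before and after PAE by McNemar's test and gives no post-PAE window. It also reports minor complications at 1 month.

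**The concern.** PAE is given once, so wording built around discontinuing a treatment has no obvious meaning here. A site that follows 7.2 and 7.3.1 literally may close its AE record long before the visits at which it is told to assess AEs. A site that follows 9.3.1 will keep recording. With three sites, both could happen in the same trial.

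What is at stake is a stated secondary aim: whether PAE produces fewer adverse events than medication. If late post-PAE events are left out, the error runs in one direction only, towards PAE.

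**Working it through.** The plan gives no figure to reproduce. The check sets the windows side by side and then works out the direction of any effect.

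**Step 1: where the window closes.**
- Treatment = PAE on day 0: 0 + 30 = day 30.
- Treatment = BPH medication, which Section 4.1.4 has stopped by the 3-month visit: 90 + 30 = about day 120, assuming a stop at about day 90. A subject who stops earlier would have an earlier close.

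**Step 2: compare with the AE time points.** Visit ranges follow from the +/- 14 days in 4.1.10 and 4.1.11.

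| AE time point | Days | Closes at day 30 | Closes at about day 120 |
|---|---|---|---|
| 3-month outcome (2.3.2) | to about 90 | days 30-90 outside | inside |
| 3-month visit | 76-104 | 46-74 days after close | inside |
| 6-month visit | 166-194 | 136-164 days after close | 46-74 days after close |
| Section 9.3.1, all AEs | no limit | conflict | conflict |

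The 6-month assessment and 9.3.1 conflict with the window on both readings. The 3-month outcome and visit conflict only on the day-30 reading.

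**Step 3: can another instrument fill the gap?** The questionnaire in Appendix 12.2 asks about the last month. At the 3- and 6-month visits it covers roughly days 60-90 and 150-180. On its own it would miss roughly days 30-60 and 90-150. The AE evaluation at those visits is not restricted to the questionnaire, so this shows only that the form alone does not settle the matter.

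**Step 4: direction of the effect.** In the Section 8.3 comparison a patient counts once if he has at least one AE in the period. Shortening the post-PAE period can turn a yes into a no, but never a no into a yes. For the pairs:
- AE both before and after can become before only, so the before-only count rises or stays the same.
- AE after only can become neither, so the after-only count falls or stays the same.

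Before-only minus after-only therefore rises or stays the same, which favours PAE.

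**Step 5: size.** This needs the number of patients whose only post-PAE AE begins after the window closes. The documents do not give it. Sections 4.1.8 and 4.1.9 expect most procedural complications to be evident by the 1-day and 1-week contacts, which points to a modest effect.

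**The case against.** The strongest reply is that Section 7 is a drug and contrast-agent section: its heading says so, its AE definition concerns subjects given a pharmaceutical product, and 7.2 asks for the relationship to the study drug. On that view the 30-day limit never governs PAE events, and 9.3.1 together with the visit schedule requires them to be recorded. The 30-day window also matches the 1-month summary of minor complications in 8.3.

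Much of this stands, and it rules out three stronger readings that a reader might infer:

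- *That events after day 30 need not be recorded.* Section 9.3.1 says all are recorded, and 4.1.10, 4.1.11 and 4.3 require assessment at 3 and 6 months. The duty is contradictory, not absent.
- *That late major complications would escape the stopping rule.* The rule in 8.1 counts complications by an outcome grade. Section 9.3.1 has complications graded and put on the CRF with no day limit, and nothing sends that count through 7.3.1.
- *That the share of days outside the window, (90 - 30)/90 = 67%, measures the undercount.* That would need events spread evenly over time, against 4.1.8 and 4.1.9. It would also count events, whereas McNemar's test counts patients, and one with an early AE is already counted.

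The reply does not remove the contradiction. Section 7 holds the protocol's only AE and SAE definitions and its only stated recording window. If it does not apply to PAE, ordinary procedural events have neither. Section 6 has no end date, but it covers only unanticipated device effects and unanticipated problems, so a late complication of a kind already listed in 5.4 may not qualify. And 9.3.1 is a general sentence that conflicts with two specific requirements without saying which prevails.

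**Conclusion.** The point holds as an internal contradiction. Sections 7.2 and 7.3.1 end recording at a moment that is undefined for a one-time procedure, and both plausible readings conflict with the 6-month AE assessment and with 9.3.1. On the day-30 reading, which is the natural one if treatment is PAE, the window also conflicts with the 3-month AE outcome and the 3-month assessment.

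If the limit were applied to PAE events, the bias in the AE comparison would be zero or in favour of PAE. That rests on two conditions: that sites follow Section 7 rather than 9.3.1, and that some patients have their only post-PAE AE after the window closes. No percentage can be defended from the documents, and the effect is probably modest. The correction is still worth making, because the error can run only one way on a stated secondary aim and the remedy is cheap.

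**What to change.** Reconcile 7.2 and 7.3.1 with 2.3.2, 4.3 and 9.3.1:

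1. Replace the 30-day limit with one recording window from the PAE procedure at least through Visit 6, for all AEs and SAEs, whether related to device, procedure or drug. Anchoring it to the procedure removes the undefined end of treatment.
2. State in 8.3 that the 2.3.2 outcome uses the first 3 months of that window.
3. State in 8.1 that the major-complication count is not limited by the 30-day window. Do not tie it to a record that ends at Visit 6: follow-up runs to 12 months, and this would add a cut-off that the protocol does not now have.

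The visits already take place, so the cost is protocol wording and a few more AE entries. The reported AE rate after PAE may be somewhat higher.

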7.3 SAEs or Serious SARs

7.3.1 Timing

After informed consent but prior to initiation of study medications, only SAEs caused by a protocol-mandated intervention will be collected (e.g. SAEs related to invasive procedures such as biopsies, medication washout).

For any other experience or condition that meets the definition of an SAE or a serious SAR, recording of the event must begin from day 1 of study treatment and continue through the 30 day follow-up period after treatment is discontinued.

7.3.2 Documentation and Notification

These events (SAEs or Serious SARs) must be recorded within 24 hours of learning of its occurrence.

7.3.3 Reporting

IRB Reporting Requirements:

The UNC-IRB will be notified of all SAEs that qualify as an Unanticipated Problem as per the UNC IRB Policies using the IRB's web-based reporting system within 7 days of the Investigator becoming aware of the problem.

8.0 STATISTICAL CONSIDERATIONS

8.1 Study Design/Study Endpoints

The primary study aim is to determine if PAE is as effective as medication (non-inferiority) in reducing urinary symptoms due to BPH at 6 months.

This will be a single arm, non-blinded study of PAE using HydroPearl Beads in a small population with BPH to assess a clinically significant reduction in medications at 6 months. After IRB approval of a written informed consent and over, approximately a 24 month duration, N=30 subjects will be recruited. Only subjects ≥ 40 years will be screened for study recruitment. Clinical procedures and evaluations will consist of a preoperative screening assessment to determine if the potential study subject meets the inclusion and exclusion criteria, enrollment, surgical procedure for prostatic artery embolization (PAE), and follow-up visits at 24 hours, 1 week, 3, 6, & 12 months. An MRI will be performed after the 6-month visit in those patients who underwent embolization to detect a change in prostatic volume and perfusion and to exclude complication.

The study will be stopped if there is greater than one major complication (Grade D, E or F) as defined by the Society of Interventional Radiology Classification System for Complications by Outcome (29).

8.2 Sample Size Rationale

Prior studies have demonstrated larger decreases in IPSS scores using PAE, compared to medication alone. Abt found the mean decrease in IPSS to be 9.23 for PAE with standard deviations of IPSS scores being 5.7 at baseline and after treatment (18). Lepor found a decrease in IPSS attributable to medications of 6.6 (17).

We set a 10% non-inferiority margin and expect the correlation of IPSS scores between screening and 6-months to be high. Assuming a correlation of .65 we will have 81.2% power to test the non-inferiority hypothesis with an alpha of 0.025 for our 30 budgeted pairs, assuming 20% dropout (pairs=subjects given single subject study design).

Power calculations used PROC POWER, SAS, Version 9.4. This sample size is adequately large to address the study's primary aim with reasonably large power.

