8.3 Data Analysis Plans

A patient will be considered an evaluable study subject evaluable for data analysis per the following criteria, a written informed consent was obtained, he meets the inclusion and exclusion criteria, and received the PAE study procedure. All subjects with 12-month follow-up data will be included for analysis even if some follow up data is incomplete. Every attempt will be made to ensure that there is as

little missing data as possible including reminder phone calls and follow-up phone calls, if a subject misses a visit.

The primary aim is to demonstrate non-inferiority of PAE compared to medication with respect to the outcome measure IPSS. We assumed a non-inferiority margin of 10%, in line with the FDA's recommendations, since similar prior non-inferiority trials were unavailable. The null hypothesis states that in the target population mean IPSS is at least 10% greater at 6 months post-treatment than at baseline (pre-treatment). The alternative hypothesis will be that the mean IPSS at 6 months is less than or equal to 10% greater than the mean IPSS at screening.

To address this hypothesis we will implement a random effects linear model, modeling IPSS score as a function of time and the indicator of whether medication had stopped by the time of the 3-month follow-up. We will include an R-side compound symmetric random effect to account for patient-level correlation. We will compute the predicted mean and standard deviation(SD) of IPSS at screening and 6 months; the difference of the predicted mean IPSS score, defined as the mean IPSS at 6 months minus the mean IPSS at screening; and the SD of this difference. Point estimates of these values will be reported along with 95% confidence intervals for the mean difference.

A non-inferiority p-value <0.05 testing whether the difference in the predicted mean at screening is at least 10% greater than the predicted mean of IPSS at screening will be considered evidence against the null hypothesis of inferiority of PAE, compared to treatment. A non-inferiority p-value >0.05 will be considered inconclusive evidence against inferiority.

As a sensitivity analysis for the primary aim, we will repeat the same model outlined above after removing patients from the analysis who were still taking medications at the 3-month follow-up. Point estimates, confidence intervals, and p-values will be compared against those obtained in the primary analysis.

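### Section 8.3 does not fix one usable primary decision rule, and the 81.2% power in Section 8.2 cannot be tied to the test that 8.3 describes

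*Combined protocol and SAP*

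**What the plan says.** Section 8.2 takes two results from earlier studies: "the mean decrease in IPSS to be 9.23 for PAE with standard deviations of IPSS scores being 5.7 at baseline and after treatment", and "a decrease in IPSS attributable to medications of 6.6". On the margin it says: "We set a 10% non-inferiority margin and expect the correlation of IPSS scores between screening and 6-months to be high". With a correlation of 0.65, 30 pairs and 20% dropout, it reports that "we will have 81.2% power to test the non-inferiority hypothesis with an alpha of 0.025", and concludes: "This sample size is adequately large to address" the primary aim.

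Section 8.3 supplies the base of the percentage: "The null hypothesis states that in the target population mean IPSS is at least 10% greater at 6 months post-treatment than at baseline". So the margin there is 10% of mean screening IPSS. The decision sentence begins: "A non-inferiority p-value <0.05 testing whether the difference in the predicted mean at screening is at least 10% greater", and the comparison it completes is again with the predicted screening mean. On reporting, 8.3 says: "Point estimates of these values will be reported along with 95% confidence intervals for the mean difference".

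Neither section says whether its alpha or p-value is one-sided or two-sided. No section gives a planning value for mean screening IPSS, and the inclusion criteria in Section 3.1 set no IPSS threshold that would bound it.

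**The concern.** Two things are at stake.

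**The decision rule.** The threshold is 0.025 in one section and 0.05 in the next, both without sidedness. Read literally, the 8.3 sentence compares a screening quantity with the screening mean, which is not the stated hypothesis. For the primary test, the analyst would have to choose the contrast and the error rate, possibly after seeing the data.

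**The power figure.** A power for a percentage margin cannot be checked without the value to which the percentage applies. Section 8.2 relies on 81.2% to call the sample adequate, yet a reader cannot tell which margin, true difference or sidedness it supports. The inputs that reproduce it point to a margin other than the one in 8.3.

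**Working it through.** **Inputs from 8.2:** SD 5.7 at both times; correlation 0.65; alpha 0.025; 30 pairs less 20% = 24; decreases of 9.23 and 6.6. **My inferences:** a paired t test, one-sided 0.025, and an advantage of 9.23 − 6.6 = 2.63 (8.2 cites both figures but does not subtract them). The medication-stopped covariate and the other visits in the 8.3 model are ignored.

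**1. Reproducing 81.2%.** SD of the paired difference = 5.7 × √(2 × 0.35) = 4.769. Power is the probability that a noncentral t with 23 df and noncentrality shift × √24 / 4.769 exceeds 2.069, where shift = advantage + margin.

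| Margin at advantage 2.63 | Shift | Power |
|---|---|---|
| none | 2.63 | 73.5% |
| 10% of 2.63 = 0.263 | 2.893 | 81.22% |
| 10% of 6.6 = 0.66 | 3.29 | 89.9% |
| 10% of 9.23 = 0.923 | 3.553 | 93.7% |

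Only the second row matches the stated figure.

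**2. What that margin means under 8.3.** If 0.263 is 10% of mean screening IPSS, that mean is 2.63. A 2.63-point advantage would put the 6-month mean at about 0, and on the 0–35 scale of Appendix 12.1 that is incompatible with an SD of 5.7 after treatment. If the margin is instead estimated from the data, the screening mean needed is 4.2. If 0.025 is two-sided, it is 5.9 (fixed margin) or 7.7 (estimated).

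**3. Other combinations that also give 81.2%.** Power depends only on the sum of advantage and margin. With a fixed margin of 10% of an assumed screening mean of 10, 15, 20 or 25, advantages of 1.89, 1.39, 0.89 or 0.39 each give 81.2%. The back-calculation is therefore not unique.

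**4. Power for the 8.3 test.** The hypothesis concerns the 6-month mean minus 1.1 × the screening mean. The SD of that contrast per patient is 5.7 × √(1 + 1.21 − 2 × 1.1 × 0.65) = 5.7 × √0.78 = 5.034. With 24 pairs, one-sided 0.025 and assumed screening means:

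| Screening mean (assumed) | Margin | Advantage 2.63: estimated / fixed margin | Advantage 0: estimated / fixed margin |
|---|---|---|---|
| 10 | 1.0 | 92.2% / 94.6% | 15.2% / 16.5% |
| 15 | 1.5 | 97.0% / 98.2% | 28.7% / 31.4% |
| 20 | 2.0 | 99.1% / 99.5% | 46.2% / 50.3% |
| 25 | 2.5 | 99.8% / 99.9% | 64.4% / 69.1% |

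**5. Effect of the threshold.** The inputs that give 81.2% at one-sided 0.025 give 89.2% at one-sided 0.05. The critical value falls from 2.069 to 1.714. The standard error of the contrast is 5.034 / √24 = 1.028, so an estimate between −1.76 and −2.13 would pass at one-sided 0.05 although the upper limit of its two-sided 95% interval is above 0.

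**The case against.** The strongest reply is that nothing has been miscalculated: 81.2% reproduces to the printed digit from figures in 8.2. That is right, and the point is not an arithmetic error. But the reproduction needs an advantage, a margin and a sidedness that 8.2 does not state, and the margin it needs is not the one in 8.3.

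It can also be said that the margin mismatch is back-solved, from variants tried with the answer known. That stands. A reader might infer that 8.2 used a wrong margin; the documents do not prove it, because the combinations in step 3 keep the 8.3 margin. Nor is 24 pairs the only conceivable count, since Section 3.0 expects all 30 to finish. With 30 pairs and a 2.63 advantage, 81.2% is reached at margins of 0.076 (estimated, one-sided 0.025), 0.217 (fixed, two-sided 0.025) or 0.375 (estimated, two-sided 0.025). These too imply very low screening means.

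A reader might infer that the trial is underpowered. The documents do not support that. Section 8.2 plans on PAE doing better than medication, and at 2.63 points the stated figure is conservative for the 8.3 test. The zero-advantage column is a sensitivity range, not the plan's scenario, although the primary objective does speak of symptom reduction similar to medication.

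Finally, a reader might call 0.025 against 0.05 a contradiction. It is an ambiguity: the planned 95% interval fits a two-sided 0.05 reading, which equals one-sided 0.025. The intended contrast can also be recovered from the hypotheses just above the decision sentence. Still, the primary decision rule should not have to be reconstructed.

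**Conclusion.** The point holds and should be fixed. Confidence is high on two parts: 8.3 does not state one usable decision rule, and 8.2 omits the screening mean, the margin in points, the assumed difference and the sidedness. Confidence is lower that 81.2% was computed for a margin other than 10% of screening IPSS. That is the likeliest reading, but it rests on the inferred 2.63 advantage and one-sided 0.025.

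The cost of the unclear threshold is bounded: the type I error is twice a one-sided 0.025 if p<0.05 is one-sided, and unchanged if it is two-sided. On power, no shortfall is shown. The true value for the 8.3 test could lie far above or far below 81.2%, depending on the unstated advantage and screening mean; the means of 10 to 25 used here are assumptions.

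**What to change.** **Section 8.3.** Replace the decision sentence with: non-inferiority is concluded if the one-sided p-value for H0: mean at 6 months − 1.1 × mean at screening ≥ 0 is below 0.025, equivalently if the upper limit of the two-sided 95% confidence interval for that contrast is below 0. Report that interval beside the one already planned for the mean difference.

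**Section 8.2.** State the planning screening mean, the margin in IPSS points (10% of that mean), the assumed true difference and one-sided 0.025. Replace 81.2% with the power for the same contrast (SD 5.034 under the stated inputs, 24 pairs), noting that the medication-stopped covariate is ignored. A second figure for a smaller advantage is optional.

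**Cost.** Rewording in two sections and one rerun of the power calculation. The hypothesis and enrolment do not change. The downside is a stricter primary test if p<0.05 was meant one-sided.
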